### **1.2 Secondary objective(s)**

1. Describe the pharmacokinetics (PK) of MEDI-573
2. Determine the immunogenicity (IM) of MEDI-573
3. Determine the pharmacodynamics of MEDI-573 on circulating plasma levels of Insulin-like growth factor (IGF)-I and IGF-II
4. Observe any anti-tumour activity of MEDI-573
5. Determine the maximum tolerated dose (MTD) of MEDI-573 in patients with advanced solid tumours, if applicable.

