### **3.1 Overall study design and flow chart**

#### **Study Design**

This is a Phase 1, open-label, single-arm, dose-escalation study to evaluate the safety, tolerability, and pharmacokinetics of MEDI-573 in Japanese adult patients with advanced solid tumours refractory to standard therapy or for which no standard therapy exists.

The study will be conducted at one site in Japan.

Subjects are considered evaluable if they receive 3 doses of MEDI-573 (Cohorts 1 and 2) or 1 dose of MEDI-573 (Cohort 3) during cycle 1 and are followed for 21 days from the date of first dose (one cycle) or they discontinue MEDI-573 due to dose-limiting toxicities (DLTs). Each cohort will include 3 to 6 evaluable subjects and a total of 9 to 18 evaluable subjects will be evaluated during the study.

MEDI-573 will be administered once every 7 days (on Days 1, 8, and 15 of each 21-day treatment cycle) as a 60-minute IV infusion in Cohorts 1 and 2 and once every 21 days (Day 1 of each 21-day treatment cycle) as a 90-minute IV infusion in Cohort 3 until unacceptable toxicity, documentation of disease progression, or other reasons for subject withdrawal. Intra-subject dose escalation will not be allowed. On 2nd Cycle and beyond, continuation, interruption or permanent discontinuation of treatment will be decided based on the criteria specified in section 5.1.8. Subjects will be considered to have completed a cycle only when they have received all the specified doses at each cycle, and subjects who do not complete a cycle will discontinue the treatment and not move on to the next cycle. Rules for interruption or discontinuation of MEDI-573 in individual subjects are described in Section 5.4.1. Rules for interruption or discontinuation of MEDI-573 and study entry are described in Section 5.4.2.

Dose escalation will follow a standard 3+3 design. Rules for dose escalation are described in Section 5.1.3.

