**Table 13**                      **Pharmacokinetic and Pharmacodynamics (Cohorts 1 and 2)**

Time for blood samples			PK	Biomarkers	
			573	antibodies	
Cycle 1	Day 1	Pre-dose	X	X	X
		End of infusion (+5 min)	X		X
		2 h after dose ( $\pm 15$ min)	X		X
		6 h after dose ( $\pm 15$ min)	X		X
	Day 2	24 h after dose of Day 1 ( $\pm 2$ h)	X		X
	Day 3	48 h after dose of Day 1 ( $\pm 2$ h)	X		X
	Day 8	Pre-dose	X		X
		End of infusion (+5 min)	X		X
	Day 15	Pre-dose	X		X
		End of infusion (+5 min)	X		X
Cycle 2	Day 1	Pre-dose	X	X	X
		End of infusion (+5 min)	X		X
	Day 8	Pre-dose	X		X
		End of infusion (+5 min)	X		X
	Day 15	Pre-dose	X		X
		End of infusion (+5 min)	X		X
Cycle 3 and beyond	Day 1	Pre-dose	X	X	X
		End of infusion (+5 min)	X		X
End of treatment			X		X
30 days after the last dose			X	X	X
3 months after the last dose				X	

Date

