**Table 14 Pharmacokinetic and Pharmacodynamics (Cohort 3)**

Time for blood samples			PK	Biomarkers	
			573 antibodies		
Cycle 1	Day 1	Pre-dose	X	X	X
		End of infusion (+5 min)	X		X
		2 h after dose ( $\pm 15$ min)	X		X
		6 h after dose ( $\pm 15$ min)	X		X
	Day 2	24 h after dose of Day 1 ( $\pm 2$ h)	X		X
	Day 3	48 h after dose of Day 1 ( $\pm 2$ h)	X		X
	Day 8	168 h after dose of Day 1 ( $\pm 2$ h)	X		X
	Cycle 2 and beyond	Day 1	Pre-dose	X	X
End of infusion(+5 min)			X		X
End of treatment			X		X
30 days after the last dose			X	X	X
3 months after the last dose				X	

The timing of the PK samples may be adjusted during the study, dependent on emerging data, in order to ensure appropriate characterisation of the plasma concentration-time profiles. The total number of samples and the total volume of blood taken from each subject will not exceed that presented in Section 6.8.1.

Collection, labelling, storage and shipment of the samples will be done in accordance with the Laboratory Manual.

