## 7.4 Calculation or derivation of pharmacokinetic variables

PK analysis of the serum concentration data for MEDI-573 will be performed by AstraZeneca K.K. The actual sampling times will be used in the parameter calculations and PK of MEDI-573 will be assessed by noncompartmental approach using a validated computer software package WinNonlin®. Descriptive statistics will be provided by dose cohort.

$C_{\max}$ ,  $C_{\max}$  at steady state ( $C_{\max, ss}$ ), time to maximum concentration ( $t_{\max}$ ) and the  $t_{\max}$  at steady state ( $t_{\max, ss}$ ) will be determined by inspection of the concentration-time profiles. Where possible the terminal elimination rate constant ( $\lambda_z$ ) after first dose will be calculated by log-linear regression of the terminal portion of the concentration-time profiles where there are sufficient data and the elimination half-life at terminal phase ( $t_{1/2\lambda}$ ) will be calculated as  $\ln 2/\lambda_z$ .

Date

The area under the curve up to the last quantifiable sample ( $AUC_{(0-t)}$ ) will be calculated using the linear trapezoidal rule. Where appropriate, the  $AUC_{(0-t)}$  will be extrapolated to infinity using  $\lambda_z$  to obtain AUC. Total clearance (CL; following the first dosing) will be determined from the ratio of dose/AUC. The volume of distribution at terminal phase ( $V_z$ ) will be determined from the mean residence time (MRT) x CL and/or the accumulation ratio ( $R_{ac}$ ) will be calculated as the ratio of the  $C_{max}$  and  $C_{min}$  on last dosing interval and first dosing interval.

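### The accumulation ratio in Section 7.4 compares each subject's last dosing interval with the first, so its dose number varies between subjects and, for weekly dosing from Cycle 3, the interval lacks a scheduled peak, trough or both

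*Protocol*

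**What the plan says.** Section 1.2 lists as a secondary objective: "Describe the pharmacokinetics (PK) of MEDI-573". Section 7.4 serves it with a noncompartmental analysis summarised by dose cohort. There, "and/or the accumulation ratio ( $R_{ac}$ ) will be calculated as the ratio of the" Cmax and Cmin "on last dosing interval and first dosing interval". No cycle or dose number is named. Section 7.4 also plans to read tmax,ss from the concentration-time profiles.

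Section 3.1 sets dosing for Cohorts 1 and 2 at "once every 7 days (on Days 1, 8, and 15 of each 21-day treatment cycle" and for Cohort 3 at "once every 21 days (Day 1 of each 21-day treatment cycle", in both cases "until unacceptable toxicity, documentation of disease progression, or other reasons for subject withdrawal".

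Table 13 (Cohorts 1 and 2) takes pre-dose and end-of-infusion PK samples at every dose in Cycles 1 and 2. In the rows for "Cycle 3 and beyond" it takes them on Day 1 only. Table 5, footnote g, agrees: Day 8 and Day 15 PK after Cycle 1 is limited to Cycle 2. Table 14 (Cohort 3) takes both samples on Day 1 in "Cycle 2 and beyond". In all cohorts the later post-dose draws (2, 6, 24 and 48 h, plus 168 h in Cohort 3) follow the first dose only. After the final dose there is an end-of-treatment sample with no stated post-dose time, and one at 30 days.

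**The concern.** An accumulation ratio has a clear meaning when everyone's numerator comes from the same dose number, or from steady state. Here the numerator is whichever interval came last, and that depends on progression, toxicity or withdrawal. Two subjects with identical kinetics can then have different Rac values only because one stayed on treatment longer. The schedule adds a second problem: for a weekly subject who reaches Cycle 3, the interval that the definition points to lacks a peak, a trough or both.

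At stake is how well the study describes build-up of exposure beyond the first dose under weekly and three-weekly dosing. With 3 to 6 evaluable subjects per cohort (Table 2), one or two long-stayers can move a cohort summary.

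**Working it through.** **1. Sample counts.** Counting time points in Table 13 gives 10 PK samples in Cycle 1, 6 in Cycle 2 and 2 per cycle from Cycle 3. Table 14 gives 7, 2 and 2. These match the PK rows of Tables 16 to 18, so the schedule has been read correctly.

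**2. Which intervals have both values.** Take the end-of-infusion sample as Cmax (an assumption, reasonable for an IV infusion) and the next pre-dose sample as Cmin.

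- Cohorts 1 and 2, intervals 1 to 6 (Cycle 1 Day 1 up to Cycle 3 Day 1): both scheduled.
- Cohorts 1 and 2, from interval 7: Day 1 to 8 has a peak and no trough; Day 8 to 15 has neither; Day 15 to the next Day 1 has a trough and no peak. The pattern repeats every cycle.
- Cohort 3: every interval closed by a further dose has both.
- Any cohort, the interval after the final dose: no following pre-dose sample, so Cmin would rest on an end-of-treatment draw at an unspecified time. A Cohort 3 subject with a single dose has the same first and last interval, so Rac says nothing.

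**3. How much the dose number matters.** The protocol gives no human half-life, so this step is an illustration under assumptions: one compartment, linear kinetics, dosing on schedule, infusion short relative to the interval. Peak and trough ratios are then equal:

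Rac(n) = (1 − r^n)/(1 − r), with r = 2^(−τ/t½).

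Weekly dosing (τ = 7 days):

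| Assumed t½ (days) | Dose 3 | Dose 6 | Dose 18 | Steady state | Steady state over dose 3 |
|---|---|---|---|---|---|
| 4 | 1.39 | 1.42 | 1.42 | 1.42 | 1.03 |
| 7 | 1.75 | 1.97 | 2.00 | 2.00 | 1.14 |
| 14 | 2.21 | 2.99 | 3.41 | 3.41 | 1.55 |
| 21 | 2.42 | 3.64 | 4.77 | 4.85 | 2.00 |

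The last column is 1/(1 − r³) = 1/(1 − 2^(−21/t½)). For 4 days that is 1/(1 − 0.0263) = 1.027; dividing the rounded entries, 1.42/1.39, gives 1.02. For 14 days it is 1/(1 − 0.354) = 1.55.

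Steady state is a limit. Within the fully sampled range, dose 6 over dose 3 equals 1 + r³: 1.03, 1.125, 1.35 and 1.50 for the four half-lives.

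Three-weekly dosing (τ = 21 days), dose 2 and dose 6: 1.03 and 1.03; 1.12 and 1.14; 1.35 and 1.54; 1.50 and 1.97. The effect is smaller: 1.54/1.35 = 1.14 at 14 days and 1.97/1.50 = 1.31 at 21 days.

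**4. tmax,ss.** After the first dose, each dosing day has only a pre-dose and an end-of-infusion sample. The recorded tmax,ss will therefore be the end of infusion in practically every subject, whatever the true profile.

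**The case against.** The best counter-argument is that Rac needs only Cmax and Cmin, and these are scheduled for the first six weekly intervals and for every completed three-weekly interval. A reader might infer from step 2 that the schedule never captures what Rac needs, or that accumulation cannot be described in this study. The tables do not support either inference. That part of the objection stands in full.

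Section 7.4 also does not require peak and trough to come from one interval. From Cycle 3 each Day 1 still gives a trough (closing the Day 15 interval) and a peak (opening the next), so two separate ratios remain obtainable. This stands too, but it means reading the last interval as the most recent sampled values, and the dose number still differs between subjects.

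It can be said that the choice of interval belongs in an analysis plan, and that a note under Table 14 lets PK sample times be adjusted. The protocol does more than leave the choice open, however: it names a subject-specific interval. Section 7.9 promises an analysis plan only if needed. The adjustment is discretionary and capped by Section 6.8.1, where Table 18 allows two PK samples per cycle from Cycle 3, and it would not make the last dose the same dose for everyone.

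On size, the 55% depends on a 14-day half-life and an unlimited number of doses; with a short half-life the effect nearly vanishes. Under the literal reading, a subject who stops after Cycle 1 has no third-interval trough, so for that subject the contrast applies to the peak ratio only. On consequences, no formal comparison of Rac between regimens is planned, Rac is not named in the escalation rules, and Section 7.9 lists all data by cohort, so the dose number behind each value should be recoverable. These limits are fair and set the weight of the point.

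**Conclusion.** The concern holds in limited form. Section 7.4 ties Rac to an interval that varies with time on treatment. For weekly dosing from Cycle 3 that interval has no scheduled peak-trough pair, and after the final dose no cohort has a scheduled trough. A cohort summary therefore mixes different points of accumulation. Under the stated model, steady-state weekly Rac exceeds third-dose Rac by about 3%, 14%, 55% or 100% for assumed half-lives of 4, 7, 14 or 21 days. The documents do not say which applies.

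A reader might go further and call tmax,ss wrong. It is uninformative under this schedule, not incorrect. The point is minor: it concerns a secondary, descriptive parameter and does not touch the primary safety objective.

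**What to change.** In Section 7.4, replace the last dosing interval with a prespecified interval that is the same for all subjects in a cohort, each divided by the first-dose interval:

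- Cohorts 1 and 2: Cycle 2 Day 15 end of infusion with Cycle 3 Day 1 pre-dose (sixth dose).
- Cohorts 1 and 2, additionally: Cycle 1 Day 15 end of infusion with Cycle 2 Day 1 pre-dose (third dose), labelled by dose number, so that subjects who leave before Cycle 3 still contribute.
- Cohort 3: Cycle 2 Day 1 end of infusion with Cycle 3 Day 1 pre-dose (second dose).

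Report the Cmax ratio and the trough ratio separately. State that tmax,ss will not be interpreted, because only pre-dose and end-of-infusion samples exist after the first dose.

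All these samples are already in Tables 13 and 14, so the change needs no extra blood, visit or dose. Its cost is that subjects who leave before the fixed interval give no Rac for it. That loss could be noticeable: a tumour assessment is required before Cycle 3 treatment (footnote c of Tables 5 and 9), and going on to Cycle 2 needs separate consent (Section 5.1.9). Separate ratios limit it, since a subject can give the peak ratio without the following pre-dose sample.

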## **7.5 Calculation or derivation of immunogenic variables**

Immunogenicity of MEDI-573 will be assessed and summarized descriptively by cohort.

## **7.6 Calculation or derivation of exploratory research variables**

Exploratory biomarkers may include evaluation of MEDI-573 on levels of circulating soluble protein biomarkers including GH, IGFBP, insulin and glucose. Additionally, we will assess levels of phosphorylated and/or unphosphorylated factors in specimens. These factors may include but are not limited to IGF-IR, IRS-1, MAPK, IR, Ki67, caspase 3, and/or AKT in archived tumour biopsies, biopsies obtained during surgical procedures conducted in the course of routine patient care and/or when archival tumour samples are available. The evaluation of cell mortality by TUNEL analysis may also be performed. And, we evaluate the relationship of IGF pathway-related components at mRNA level, including IR-A mRNA level (IGF-I, IGF-II, INSR, IR-B, IR-A, IGF-IR, IGF-IIR, IRS-1, IRS-2, IGFBP-1, IGFBP-2, IGFBP-3, IGFBP-4, IGFBP-5, IGFBP-6) in tumour biopsies obtained pre- and post-MEDI-573 treatment using qRT-PCR assays or microarray studies.

Results from the exploratory biomarker and pharmacogenetic research will be reported separately from the Clinical Study Report for the main study.

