### **Adverse events based on examinations and tests**

The results from protocol mandated laboratory tests, vital signs, ECGs and other safety assessments will be summarised in the Clinical Study Report. Deterioration as compared to baseline in these parameters will therefore only be reported as AEs if they fulfil any of the criteria for a SAE or DLT, or are the reason for discontinuation of treatment with the investigational product unless clearly due to progression of disease under study (see Disease progression).

If deterioration in a laboratory value, vital sign, ECG or other safety assessment is associated with clinical signs and symptoms, the sign or symptom will be reported as an AE and the associated laboratory result or other finding will be considered as additional information.

Date

Wherever possible the reporting investigator uses the clinical, rather than the laboratory term (eg, anaemia versus low haemoglobin value).

Deterioration of a laboratory value that is unequivocally due to disease progression should not be reported as an AE.

Any new or aggravated clinically relevant abnormal medical finding at a physical examination as compared with the baseline assessment will be reported as an AE.

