## **6.7 Exploratory research**

### **6.7.1 Exploratory biomarker research**

If a subject agrees to participate in the exploratory biomarker research component of the study biological samples (eg, plasma, serum, archived and study-obtained tumour, etc) will be collected and may be analysed for exploratory biomarkers to assess correlations with disease activity, effects of investigational product and clinical outcomes.

The results of this exploratory biomarker research will be reported separately and will not form part of the Clinical Study Report.

The results of this exploratory biomarker research may be pooled with biomarker data from other studies with the investigational product to generate hypotheses to be tested in future studies.

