## **7. EVALUATION AND CALCULATION OF VARIABLES AND STATISTICAL METHODS**

### **7.1 Definition of study endpoints**

To meet the objectives for this study, data for the following endpoints will be collected:

- Safety and Tolerability (Primary)
- MTD and/or optimal biologic dose, if possible (Secondary)
- MEDI-573 PK (Secondary)
- IM (Secondary)
- Pharmacodynamics (Secondary)
- MEDI-573 Tumour response (Secondary)
- Exploratory biomarkers (levels of circulating soluble protein biomarkers including GH, IGF1, insulin and glucose, and levels of phosphorylated and/or factors biomarkers in specimens including IGF-1R, IRS-1, MAPK, ERK, Ki67, caspase 3, and/or AKT) (Exploratory)
- Pharmacogenetics (Exploratory)

Safety endpoints are defined in Sections 6.3 and 6.4. Calculations and analysis plans for each of these endpoints are presented below.

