### 7.3.1 Other significant adverse events

During the evaluation of the AE data, a medically qualified expert will review the list of AEs that were not reported as SAEs and AEs leading to discontinuation of investigational product. Based on the expert's judgement, AEs of particular clinical importance may, after consultation with the Global Safety Physician, be considered OAEs and reported as such in the Clinical Study Report. A similar review of laboratory values, vital signs, ECGs and other safety assessments will be performed for identification of OAEs.

Examples of these are marked haematological and other laboratory abnormalities, and certain events that lead to intervention (other than those already classified as serious), dose reduction or significant additional treatment.

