## **7.9**                      **Methods of statistical analysis**

The statistical analyses will be performed using SAS under the direction of the Biostatistics group, AstraZeneca. Other tools may be used for exploratory summaries and graphical presentations. A comprehensive statistical analysis plan will be finalized prior to the clean file meeting if necessary.

All data will be provided in data listings sorted by dose cohort. Continuous variables will be summarized by descriptive statistics including N, mean, standard deviation, median, and range. Descriptive statistics for summarizing categorical variables include frequency and percentage. Figures may be prepared if necessary. Missing data will be treated as missing and no data will be imputed.

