### **7.10**                      **Timing of the analysis**

#### **7.10.1**                      **Main analysis**

There will be an interim data cut-off defined as the earlier of 6 months after the last subject recruited starts investigational product or 3 months after the final subject discontinues investigational product. These data will be used for the statistical analysis and detailed in the Clinical Study Report (CSR). The main conclusions on the primary, secondary, and exploratory objectives of this study will be made on the basis of these data.

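### If glucose is measured at the early post-infusion draws, Sections 6.7.1 and 7.6 send it outside the CSR, although no scheduled on-treatment safety glucose falls within 24 h after an infusion

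*Protocol*

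**What the plan says.** **Reporting rule.** Section 6.7.1: "The results of this exploratory biomarker research will be reported separately and will not form part of the Clinical Study Report". Section 7.6 repeats it: "Results from the exploratory biomarker and pharmacogenetic research will be reported separately from the Clinical Study Report for the main study".

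**Glucose as an exploratory biomarker.** Objective 1 in Section 1.3 and Section 7.6 (as something that may be evaluated) both name it. The endpoint list in Section 7.1 refers to "levels of circulating soluble protein biomarkers including GH, IGF1, insulin and glucose". Table 15, which sits under Section 6.7.1.2, assigns GH, insulin and glucose to the clinical laboratory. Tables 5 and 9 schedule only an Insulin/GH row, with Section 6.7 as its reference.

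**Glucose as a safety test.** Section 6.3.5 lists glucose in clinical chemistry and requires laboratory tests on treatment days to be done before the infusion.

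**Laboratory adverse events.** The part of Section 6.4.3 on examinations and tests says: "The results from protocol mandated laboratory tests, vital signs, ECGs and other safety assessments will be summarised in the Clinical Study Report". For that reason it limits laboratory adverse events to changes that are SAEs, DLTs or the cause of discontinuation. Associated signs and symptoms are reported in their own right.

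**DLT.** Section 5.1.4 excepts a fasting glucose rise below Grade 4 that lasts under 24 hours after administration.

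**The concern.** Safety is the primary objective, and Section 5.3 cites hyperglycaemia, including Grade 3, with other agents aimed at this pathway. It also presents sparing of glucose homeostasis as a potential advantage of MEDI-573. Glucose in the first day after an infusion bears directly on that expectation.

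Section 6.4.3 can restrict laboratory adverse events because the laboratory results themselves appear in the CSR. If early post-infusion glucose exists only as exploratory data, and exploratory data are reported elsewhere, that premise is not secured for these values. A short rise could then be neither an adverse event nor part of the CSR laboratory summary.

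The dose escalation committee is affected in the same way. Section 5.1.3 lets the sponsor choose an intermediate dose because of toxicities below the DLT threshold, but an asymptomatic laboratory change of this kind would not reach the committee as an adverse event.

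**Working it through.** The check counts scheduled draws and classifies each by nominal time since the last infusion. No error rate or sample-size formula is involved.

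**1. The plan's own counts.** Table 16 (screening plus Cycle 1) gives 5 clinical chemistry samples in Cohorts 1 and 2 and 4 in Cohort 3. It gives 10 and 7 soluble-protein samples for the clinical laboratory.

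- Table 5 chemistry: screening, Days 1, 3, 8, 15 = 5. Table 9: screening, Days 1, 3, 8 = 4. Both match.
- Table 13 biomarker draws in Cycle 1: 6 times from Day 1 pre-dose to 24 h (pre-dose, end of infusion, 2 h, 6 h, 24 h) and Day 3 (48 h), plus pre-dose and end of infusion on Days 8 and 15: 6 + 4 = 10. Table 14: the same 6 plus Day 8 (168 h) = 7. Both match.
- Blood totals: 25 + 13 + 40 + 8.5 + 160 + 50 + 3.5 = 300 mL. Cohort 3: 20 + 10.4 + 28 + 8.5 + 112 + 35 + 3.5 = 217.4 mL. Both match.

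**2. Safety glucose within 24 h after an infusion.** Dosing-day samples are pre-infusion and Day 2 has no chemistry. The first safety sample after the first infusion is on Day 3, about 48 h. From Cycle 2, Section 5.1.8 keeps doses at least 6 days (Cohorts 1 and 2) or 20 days (Cohort 3) apart, so a pre-dose sample cannot fall within 24 h of the preceding infusion. The Cohort 3 Day 8 sample, with its window of 2 days either way, cannot either. The count is 0 in every cycle and cohort. End-of-treatment, follow-up and unscheduled tests are not counted.

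**3. Clinical-laboratory draws in the same window, per subject in Cycle 1.**

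| | End of infusion | 2 h, 6 h, 24 h on Day 1 | Within 24 h | All Cycle 1 draws |
|---|---|---|---|---|
| Cohorts 1 and 2 | 3 | 3 | 6 | 10 |
| Cohort 3 | 1 | 3 | 4 | 7 |

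An end-of-infusion sample says little about the following day. From Cycle 2 every draw in the window is of that kind. The informative draws are therefore the three on Cycle 1 Day 1.

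**4. Trial total.** With all three cohorts filled and every subject taking part: 3 × 9 = 27 to 3 × 18 = 54 informative draws. Adding end-of-infusion draws gives 6 × 6 + 3 × 4 = 48 to 12 × 6 + 6 × 4 = 96 in Cycle 1, of which 48 − 27 = 21 to 96 − 54 = 42 are end-of-infusion samples.

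**5. What the counts do not show.** Matching counts fix the draw times, not the analytes. Glucose in those tubes is inferred from Table 15. If it is absent, the number of glucose values is 0. If participation is voluntary, the number lies between 0 and 54.

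**6. Section 5.1.4.** Telling a rise of under 24 hours from a longer one needs readings inside 24 hours. The safety schedule has none, so its duration could be timed only from the clinical-laboratory draws or from unscheduled tests.

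**The case against.** The strongest reply is that the exclusion may not reach these values. Glucose at the post-infusion draws is never stated, and Section 7.6 says only that it may be evaluated. Tables 16 to 19 reserve the exploratory biomarker label for the sponsor's central laboratory and give the clinical laboratory a separate row. Only tumour samples are marked optional in Tables 5 and 9, so the blood draws could be read as protocol-mandated tests that belong in the CSR. Other text points the same way. Section 7.9: "All data will be provided in data listings sorted by dose cohort". Section 7.10.1, on the data set behind the CSR: "The main conclusions on the primary, secondary, and exploratory objectives of this study will be made on the basis of these data". Section 7.3.1: "A similar review of laboratory values, vital signs, ECGs and other safety assessments will be performed for identification of OAEs".

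Part of this stands. The protocol is ambiguous, and a listing or the review for other significant adverse events might catch a rise. But Table 15 lies within Section 6.7.1, the Insulin/GH row refers to Section 6.7, and Section 7.6 names glucose just before its separate-reporting rule. None of the other provisions assures a place in the CSR laboratory summary. Section 6.7.1 also opens with "If a subject agrees to participate in the exploratory biomarker research component of the study", which sits badly with calling the draws mandated. If glucose is not in those tubes, nothing is diverted, but the schedule then holds no glucose within 24 h at all.

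A second reply is that the gap is narrow, and this stands in full. In monkeys, IGF suppression lasted one to two weeks depending on dose (Section 2.2.1), so a lasting effect on glucose would be expected to show at Day 3 or later. Subjects must be willing to stay in hospital for at least a week after starting treatment, Grade 3 laboratory values are repeated, and the committee reviews all available safety data. Urine glucose and HbA1c are also scheduled, though neither is sensitive to one brief rise.

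A third reply is that table layout, fasting fields and grading rules belong in the SAP or CRF. That is right, and they are not part of the point. The separate-reporting rule is: it is stated in the protocol and not merely left open.

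**Conclusion.** The point holds, with minor importance. As written, Sections 6.7.1 and 7.6 direct exploratory glucose away from the CSR, while no scheduled on-treatment safety glucose falls within 24 h after an infusion. Assuming that glucose is measured at the clinical-laboratory draws, that all three cohorts are filled and that every subject takes part, 27 to 54 informative values are concerned, 3 per subject.

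The effect is limited to rises that are brief, asymptomatic, non-serious, below the DLT threshold and not a cause of discontinuation. A reader might infer that the trial would miss important hyperglycaemia, or that its DLT count and MTD are unsound. The documents do not support that: DLTs, SAEs, discontinuations and symptomatic events reach the CSR, lasting rises would appear in safety chemistry from Day 3, and nothing in the protocol shows that MEDI-573 causes brief rises. Nor should a reader take it as established that 48 to 96 post-infusion glucose values are being withheld. That range counts draws, includes 21 to 42 end-of-infusion samples, and rests on an analyte that Tables 5 and 9 do not name.

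**What to change.** - Exempt clinical-laboratory glucose from the separate-reporting sentences in Sections 6.7.1 and 7.6.
- Name glucose in the Insulin/GH row of Tables 5 and 9.
- Summarise the available values in the CSR safety laboratory section by cohort and nominal time, with the number of subjects contributing at each time.
- Give the Cycle 1 values to the dose escalation committee.

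The cost is protocol wording and one further CSR table. No new blood draw is needed, because the clinical-laboratory draws are already in Tables 16 to 18. Reporting for whoever has values leaves consent unchanged. The downside is interpretation: values at 2 h and 6 h may reflect a meal, and steroids given for an infusion reaction (Section 4.3.1) can raise glucose.

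A fasting-status field, grading rules for non-fasting samples and a statement that the draws are core are optional. Making voluntary draws core would require a change to the consent text.
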